6.1 Outcome definitions

Primary variables:

- First primary: Serious COVID-19 (MSIS-confirmed COVID-19 with dyspnoea, hospitalisation, or death)
- Second primary: COVID-19 defined by positive PCR obtained from MSIS
- Third primary: A negative SARS-CoV-2 test (MSIS).
- Fourth primary: Self-reported airways infection

The first incidence of report of any of the above primary variables will be used in the analyses. The specified order will be used for the fallback analyses. The values of all variables will be Yes/No to the condition together with time from one week after start of oil consumption to first reporting of the condition, i.e. Yes (except for third primary variable, where total number of negative tests is reported). Those not reporting a Yes answer, the last reported time will be used as censoring time. The date from one week after oil-consumption starts to the date of reporting of a Yes will be converted to number of days from the first to the second date.

The primary analysis set is the defined ITT sample with missing data on outcome counting as the negative outcome.

Compliance

For sensitivity analyses on compliance, we will define compliant participants as those having taken CLO for at least 2 months. We will also analyse participants based on volume CLO taken (more than 250 ml).

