6.2 Analysis methods

The first, second and fourth primary variables will be analysed for relative risk (risk ratio) of acquiring a condition using cod liver oil versus corn oil using the Wald test³. Time to first occurrence of the primary variables will be plotted using the Kaplan-Meier approach. The third primary variable will be compared for the two treatment groups tested using study duration-adjusted counts. If the use of student's t-test cannot be used due to underlying assumptions not holding up, a median test will be used. If appropriate, the Cox proportional hazard regression will be used to assess the effect of the outcome of the above specified baseline variables on time to occurrence of the primary variables. Otherwise, logistic regression on the occurrence of outcome will be undertaken with the same explanatory variables. The explanatory variables to be included in the main regression analyses are:

- Age at CLOC screening
- Gender
- BMI

³ © SAS Institute Inc. https://documentation.sas.com/doc/no/pgmsascdc/v_016/statug/statug_freq_details70.htm, 18-Aug-2021

- Occupational status (employed/not employed?)
- Children at home (Y/N)
- Chronic disease (Y/N ≥ 1 chronic diseases)
- Dietary intake (Y/N)
 - Cod liver oil
 - Vitamin D
 - Omega 3
 - Fish consumers
- Present smoker (Y/N)

Other variables will be included in ad hoc/exploratory analyses.

The sample size in this study is so large that normal assumptions are likely to be valid. If this should not be appropriate for specific variables, appropriate non-parametric alternatives will be used. Should the assumptions to use Cox proportional hazard model not be satisfied, an alternative approach is logistic regression. The assumptions for methods used will be assessed. Should they be violated and not rectified by the sample size, alternative approaches will be used.

Sensitivity analyses will be conducted by including subsets of the study sample based on compliance. Other baseline variables may also be proposed as basis for ad hoc sensitivity analyses. Overdispersion will be considered for models where that can be an issue.

Further ad hoc subgroup analyses may be performed based on the findings of the primary analyses.

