 - NA = has not filled out form

- Death criteria

- Participant registered as dead/deceased in the National Population Register after a positive cov test (MSIS), but only if the death was related to COVID-19 based on hospital records or information from relatives.

- **Second primary:** New MSIS positive

- *CLOC_primary_2_msis_status*
 - Created from *MSIS_CLOC_test_status*
 - 1 = tested positive for the first time during **CLOC participation period**
 - 2 = only tested negative during **CLOC participation period** (never positive)
 - 3 = untested during **CLOC participation period** (never positive)
- Participants who have tested positive within one week after start of oil consumption are excluded from the analysis (*exclude_Msis_transtart7d*).
- MSIS criteria
 - Variable: *MSIS_CLOC_test_status*
 - 1 = tested positive for the first time during CLOC
 - 2 = only tested neg during CLOC (never positive)
 - *Variables obtained through MSIS (translated): “Test date” and “Test result”*
 - Variable to be analyzed as second primary endpoint identifying only tests registered during the **CLOC participation period** (defined as period from start of cod liver oil/placebo consumption (*deriv_Date_CLO_start_corr*) to June 2, 2021).
- **Third primary: Negative test**
 - *CLOC_primary_3_negative_tests*
 - Generated from *MSIS_CLOC_TotalTests_7d_neg*
 - Sum of total negative tests registered during the period from one week after start of cod liver oil/placebo consumption (*deriv_Date_CLO_start_corr*) to June 2, 2021.
 - 0 if no tests registered
 - Negative test criteria
 - Variable: *MSIS_CLOC_TotalTests_7d_neg*
 - Sum of total negative tests registered during the period from one week after start of cod liver oil/placebo consumption (*deriv_Date_CLO_start_corr*) to June 2, 2021.
 - Supplementary variables
 - *MSIS_CLOC_FirstNegative*
 - Date of first negative test registered during the **CLOC participation period**.
 - *MSIS_CLOC_LastNegative*
 - Date of last negative test registered during the **CLOC participation period**.
- **Forth primary: Self-reported airway infections**
 - *CLOC_primary_4_selfrep_airway*
 - Generated from *deriv_respinf_date_yn*
 - 1 = ever answered yes and provided valid date in any form
 - 0 = only answered no, or provided non-valid date in any form
 - 999 = has filled out form, has not answered airway infections question
 - NA = has not filled out form

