 - Any self-reported airway infections during the period from one week after start of cod liver oil/placebo consumption (*deriv_Date_CLO_start_corr*) to June 2, 2021.
 - Self-reported airway infections criteria
 - Variable: *deriv_respinf_date_yn*

- Answered question *has had respiratory infection since last cloc report* in any CLOC questionnaire (R1-R6)
 - *deriv_respinf_report_yn_ever*
- Date of self-reported airway infections in the period from one week after start of cod liver oil/placebo consumption (*deriv_Date_CLO_start_corr*) to June 2, 2021.
 - *deriv_respinf_date_sums*
-
- Supplementary variable
 - *deriv_respinf_count_report_sum*
 - Number of respiratory infections reported
 - *Rx_Date_respiratoryinfectionx_sym_start_report*
 - Date of each infection reported in each report form

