All blood- and other biological samples collected as part of the study will be stored in this biobank.

Questionnaires and consent forms

Participants will already have completed the Koronastudien questionnaires containing questions about risk factors for Covid-19, supplement use, travel history, cancer, cardiovascular disease, and other previous diseases, skin-type, sunlight exposure, and demographic variables). During the study period, it is expected that 1-2 Koronastudien specific follow-up questionnaires will be distributed, and these will be coordinated to reduce the burden of participation. In addition, the following data will be collected from the sub-study participants using electronic forms:

- Screening questionnaire before inclusion (inclusion and exclusion criteria)
- Consent form. The identity of each participant in Koronastudien is known through the consenting procedure using two-factor authentication with Bank ID. The consent form for Transtudien will be sent as a unique link to existing participants, and consenting will be a simple yes or no checkbox at the end of the form without requiring further identification with Bank ID.
- Baseline questionnaire: Diet including an estimate of vitamin D and n-3 LCPUFA intake and other baseline data collection will be coordinated with a follow-up questionnaire in Koronastudien to reduce participant burden.
- Every month: Compliance, use of supplements, side effects, efficacy of blinding, endpoints
- End of study: FFQ (a validated web-based food frequency questionnaire), risk factors for Covid-19 and other relevant diseases, use of supplements, previous conditions, side effects, efficacy of blinding, endpoints
- Follow-up up to two years: Diet, use of supplements, endpoints.

Participants will also be encouraged to report any symptoms of respiratory tract infections and any possible side-effect during the cod liver oil taking period using an electronic questionnaire available to them at all times during the study period.

Dietary questions on vitamin D and n-3 LCPUFA will be based on the FFQ.

Registries

Data for validation of endpoints, previous diseases, and risk factors will be obtained from the following registries (registry, data to be obtained):

- Causes of death: death, and cause of death
- Hospital records: verification of endpoints
- KUHR: visits to GP and cause of visit
- Norwegian Prescription database:, medications

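### SAP 6.1 times events by the report date although onset and test dates are held, so form-based event times run late and lump at the questionnaires

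*SAP*

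**What the plan says.** **Event time.** SAP 6.1 gives the first, second and fourth primary variables a yes/no value plus a "time from one week after start of oil consumption to first reporting of the condition". It repeats the rule when converting to days: "The date from one week after oil-consumption starts to the date of reporting of a Yes will be converted to number of days". The third primary variable is a count and is outside this point.

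**Censoring.** For participants without a Yes, "the last reported time will be used as censoring time".

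**Analysis.** SAP 6.2 uses a different term: "Time to first occurrence of the primary variables will be plotted using the Kaplan-Meier approach". Its Cox model is likewise described as a model of time to occurrence. Section 9 of the protocol (Analysis sets) also lists Kaplan-Meier plots and Cox regression for the primary endpoints.

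**Dates held.** SAP Appendix 1 lists the test date and result among the MSIS variables. For endpoint 4 it defines the qualifying event by the "Date of self-reported airway infections in the period from one week after start of cod liver oil/placebo consumption" up to 2 June 2021, and it lists a symptom-start variable described as the "Date of each infection reported in each report form". An endpoint 4 Yes requires a valid date; a non-valid date is coded 0.

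**Source of the reports.** Endpoint 4 is built from forms R1-R6, which ask about infection since the previous report. The dyspnoea and hospitalisation parts of endpoint 1 come from forms submitted after the positive MSIS test. Section 8 of the protocol gives the schedule: "Every month: Compliance, use of supplements, side effects, efficacy of blinding, endpoints". It also offers a symptom form that is open at all times.

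**The concern.** The SAP defines one time variable in 6.1 and names another in 6.2, and Appendix 1 defines no time-to-event variable that would settle which is meant. Followed literally, 6.1 dates an airway infection by the form that mentions it. Whether that infection counts at all is decided by its onset date. The yes/no value and the time value of one endpoint therefore rest on different dates.

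Where the report comes on a periodic form, the recorded time is always later than the event, and events from a whole interval share a few days. The Kaplan-Meier curve then steps at the forms and understates early incidence. The check of proportional hazards, on which 6.2 makes the choice between Cox and logistic regression depend, would be run on those times. SAP 3.5 gives participation as one to six or more months, so a delay of several weeks is a visible part of follow-up.

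**Working it through.** **1. What does not use event times.** The documents give no figure for event timing. Their sample sizes are comparisons of two proportions and reproduce as such, two-sided, 1:1, with pooled variance:

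n per arm = [z(1-α/2)·√(2p̄(1-p̄)) + z(power)·√(p1(1-p1)+p2(1-p2))]² / (p1-p2)²

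- Endpoint 1 (0.25% vs 0.15%, α 0.018, power 70%): [2.3656×0.063182 + 0.5244×0.063178]² / 0.001² = 33,341.3, rounded up to 33,342 per arm, total 66,684. The plan states 67,000.
- Endpoint 2 (1.0% vs 0.8%, α 0.03, power 70%): [2.1701×0.133559 + 0.5244×0.133551]² / 0.002² = 32,376.5, rounded up to 32,377 per arm, total 64,754. The plan states 65,000.
- Endpoint 4 (30% vs 27%, α 0.001): the stated 16,000 gives 81.9% power and 23,000 gives 96.0%, in line with the stated 80% and >95%.

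Neither these sizes nor the Wald risk ratio test contains an event time.

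**2. Which endpoints are affected.**

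| Endpoint | Source of the Yes | Effect of the 6.1 rule |
|---|---|---|
| 1, dyspnoea or hospitalisation | forms after the positive test | late, lumped at forms |
| 1, death | population register | not tied to monthly forms |
| 2 | MSIS | ambiguous; may already be the MSIS date |
| 4 | forms R1-R6 | late, lumped at forms |

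**3. Size of the delay.** Assumptions, none given in the documents: six forms 30 days apart, onset even over the 180 days, each form returned independently with probability p, and an infection reported on the next returned form. The wait for the next due form averages 30/2 = 15 days, and each missed form adds 30. With q = 1-p, the relative weight of reported events that missed j forms is (6-j)·p·q^j, because only 6-j intervals still have a form left.

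- p = 1: mean delay 15 days.
- p = 0.8: weights 4.8, 0.8, 0.128, 0.0192, 0.00256, 0.000256, sum 5.7500. Mean forms missed 1.1251/5.7500 = 0.196. Delay 15 + 30×0.196 = 20.9 days. Share missing at least one form 0.9500/5.7500 = 17%.
- p = 0.6: weights 3.6, 1.2, 0.384, 0.1152, 0.03072, 0.006144, sum 5.3361. Mean forms missed 2.4672/5.3361 = 0.462. Delay 15 + 30×0.462 = 28.9 days. Share missing at least one form 1.7361/5.3361 = 33%.

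**4. Effect on the endpoint 4 curve.** Assume a 30% placebo risk at constant hazard over the 173 days from day 7 to day 180, with every form returned on its due day. True cumulative incidence at t days after the day-7 origin is F(t) = 1 - 0.7^(t/173). Forms fall at t = 23, 53, 83 and so on. On the day before a form, where the gap is widest, the report-dated curve still shows F at the previous form.

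| Day after origin | By onset | By report |
|---|---|---|
| 22 | 4.4% | 0% |
| 52 | 10.2% | F(23) = 4.6% |
| 82 | 15.6% | F(53) = 10.4% |

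All events fall on six distinct days. The curves meet again at each form.

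**5. Effect on the hazard ratio.** This was simulated for 30% vs 27%, 8,000 participants, five runs, with arm as the only covariate and the same delay in both arms. With forms on time the mean hazard ratio was 0.8543 by onset date, against 0.8542 (Efron ties) or 0.858 (Breslow ties) by report date. With forms an average of 3 or 7 days late, the two datings differed by less than 0.001.

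**The case against.** The strongest reply is that little depends on this. The confirmatory tests for endpoints 1, 2 and 4 are risk ratios, SAP 4.1 places regression outside the fallback procedure, and 6.2 uses Cox only if appropriate. The word occurrence in 6.2 suggests that the authors meant the event itself, so 6.1 may be no more than loose wording. This largely stands. It limits the point to a clarification, but an analyst who programs from 6.1 would still produce the wrong times.

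Stronger readings are tempting, and the documents do not support them:

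- **All event times are lumped at monthly forms.** Endpoint 2 comes from MSIS and the death part of endpoint 1 from a register. For endpoint 2, reporting can mean the MSIS date, in which case nothing is lumped.
- **The treatment effect is biased.** With equal delay in both arms the hazard ratio barely moves. Unequal delay could distort it, but the documents hold no delay data.
- **The delays are longer.** With no limit on later forms, 15 + 30(1-p)/p gives 22.5 and 35 days at 80% and 60% return. Endpoint 4 uses only R1-R6, and under SAP 6.3 an infection never reported counts as No, so the six-form figures apply.
- **Some event times fall after 2 June 2021.** That requires R forms submitted after that date, and submission dates are not given.
- **An early-versus-late comparison is spoiled.** None is pre-specified.

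The always-open symptom form could shorten delays, but Appendix 1 does not name it as a source for endpoint 4.

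**Conclusion.** The point holds as an inconsistency between SAP 6.1 and 6.2, with a practical effect on endpoint 4 and on the self-reported parts of endpoint 1. There the rule as written makes event times late by about 15 days on average with full return, and by about 21 or 29 days at 80% or 60% return. The 30-day spacing, even onset and return rates are assumptions, so these figures show an order of size and do not predict the delay in this trial. The damage is to the shape and timing of the Kaplan-Meier curves and to the proportional-hazards check. The risk ratio tests, alpha allocation and sample size stand as they are. For endpoint 2 the SAP only needs to say which date it means. This is a minor but worthwhile correction.

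**What to change.** In SAP 6.1, replace the report date with an event date:

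- **Endpoints 1 and 2:** the date of the first positive MSIS test. This suits endpoint 1 because section 3 of the protocol requires the dyspnoea or hospitalisation to coincide with that test.
- **Endpoint 4:** the start date of the first qualifying infection. No fallback to the report date is needed. A Yes already requires a valid date, so a fallback would either be empty or turn participants coded 0 into events.

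Change censoring in the same edit. If events are redated but non-events still leave at their last report, MSIS positives would count up to 2 June 2021 while non-cases dropped out of the risk set earlier, which can push the registry curve upward.

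- **Endpoint 2:** censor at 2 June 2021, or at earlier death or loss of registry coverage.
- **Form-based outcomes:** censor at the last date covered by a returned form, and no later than 2 June 2021. State which rule governs the death part of endpoint 1, which does not depend on a form.

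Add the resulting time variables to Appendix 1, so that 6.1 matches the term occurrence in 6.2. The cost is SAP wording and a few lines of programming. Appendix 1 already lists the test and symptom-start dates, so no new data collection is needed for the event dates.

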6.2 Analysis methods

The first, second and fourth primary variables will be analysed for relative risk (risk ratio) of acquiring a condition using cod liver oil versus corn oil using the Wald test³. Time to first occurrence of the primary variables will be plotted using the Kaplan-Meier approach. The third primary variable will be compared for the two treatment groups tested using study duration-adjusted counts. If the use of student's t-test cannot be used due to underlying assumptions not holding up, a median test will be used. If appropriate, the Cox proportional hazard regression will be used to assess the effect of the outcome of the above specified baseline variables on time to occurrence of the primary variables. Otherwise, logistic regression on the occurrence of outcome will be undertaken with the same explanatory variables. The explanatory variables to be included in the main regression analyses are:

- Age at CLOC screening
- Gender
- BMI

³ © SAS Institute Inc. https://documentation.sas.com/doc/no/pgmsascdc/v_016/statug/statug_freq_details70.htm, 18-Aug-2021

- Occupational status (employed/not employed?)
- Children at home (Y/N)
- Chronic disease (Y/N ≥ 1 chronic diseases)
- Dietary intake (Y/N)
 - Cod liver oil
 - Vitamin D
 - Omega 3
 - Fish consumers
- Present smoker (Y/N)

Other variables will be included in ad hoc/exploratory analyses.

The sample size in this study is so large that normal assumptions are likely to be valid. If this should not be appropriate for specific variables, appropriate non-parametric alternatives will be used. Should the assumptions to use Cox proportional hazard model not be satisfied, an alternative approach is logistic regression. The assumptions for methods used will be assessed. Should they be violated and not rectified by the sample size, alternative approaches will be used.

Sensitivity analyses will be conducted by including subsets of the study sample based on compliance. Other baseline variables may also be proposed as basis for ad hoc sensitivity analyses. Overdispersion will be considered for models where that can be an issue.

Further ad hoc subgroup analyses may be performed based on the findings of the primary analyses.

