3.3 Sample size

The fallback method (<https://www.fda.gov/media/102657/download>) will be used to correct for testing of multiple primary endpoints.

The total alpha (0.05) will be divided among the endpoints, and a fixed sequence for the testing will be maintained. As the testing sequence progresses, a successful test preserves its assigned alpha as "saved" (unused) alpha that is passed along to the next

test in the sequence. This passed-along alpha is added to the assigned alpha of the next endpoint, and the summed alpha is used for testing that endpoint. Thus, as sequential tests are successful, the alpha accumulates for the endpoints later in the sequence; these endpoints are then tested with progressively larger alphas.

Endpoints in testing order with power calculation:

1. Serious COVID-19 (MSIS-confirmed COVID-19 with dyspnoea, hospitalization, or death). (MSIS: Mandatory Norwegian Surveillance System for Communicable Diseases). Assigned $\alpha=0.018$.

Based on the observations in Koronastudien of a 40% reduction in serious COVID-19 in the group reporting use of cod liver oil, and an expected incidence of 0.25%, a power of 70%, 67,000 participants will have to be included for this endpoint.

2. COVID-19 positive PCR (MSIS). Assigned $\alpha=0.03$.

Based on the observations in Koronastudien of a 20% reduction in COVID-19 incidence in the group reporting use of cod liver oil, and an expected incidence of 1%, a power of 70%, 65,000 participants will have to be included for this endpoint.

3. A negative SARS-CoV-2 test (MSIS). Assigned $\alpha=0.001$.

COVID tests (SARS-CoV2-2), real time (RT)-PCR, are mostly obtained because of a suspicion of COVID-19. The number of negative COVID tests from one week after starting taking cod liver oil/placebo and to the end of the intervention period. This endpoint has been added as an alternative to the Positive PCR or bacterial culture endpoint (now a secondary endpoint, as it is not available at this time).

4. Self-reported airway infection. Assigned $\alpha=0.001$.

Based on the expected frequency of airway infections in Koronastudien of >30% and as a threshold of clinically interesting reduction of all airway infections of 10%, 23,000 participants will have to be included for this endpoint. The study has a power for this endpoint >95%. 16,000 participants in the study will give an 80% power for this endpoint.

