3.4 Framework

The background for the study is that data suggest that cod liver oil may prevent COVID-19 and complications of COVID-19. Hence, this is a superiority study, placebo-controlled, blinded and randomised, designed to show that cod liver oil has a positive effect on COVID-19 and complications of COVID-19, compared to corn oil, the placebo.

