4.1 Confidence intervals and *P* values

An overall significance level of 0.05 is used for the composite primary endpoints and are tested in the specified order as seen in section 3.3, above. To control the overall significance level pertaining to the primary hypotheses, the fallback method for alpha spending is used for the statistical analyses of relative risk comparing the two randomisation groups, Cod liver oil and Corn oil. If the first analysis results in significant results, i.e., $p \leq 0.018$, according to section 3.3, the second null-hypothesis can be tested at a significance level of $0.018 + 0.030 = 0.048$. If the first null hypothesis is not rejected, the second is tested at the stated significance level of 0.03. Each following null hypothesis to be tested has a significance level of its stated level plus the sum of the levels of previous tests that result in a significant result. Supplementary analyses, such as regression analyses, will not be part of the fallback method, as these are expected to be highly correlated to the primary analyses. Confidence interval and p-values will be provided for all variables tested statistically.

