- MSIS (the Mandatory Norwegian Surveillance System for Communicable Diseases): Covid-19 status,- negative and positive SARS-CoV-2 tests.
- The Norwegian Patient Registry (NPR): Hospital admissions and outpatient visits: fractures, health-related events and endpoints
- The patients' general practitioner or treating physician may be contacted for verification of endpoints, adverse effects, and causes of death

- Luftveisdatabasen (Airway Database), Covid-19 status, other PCR and culture verified infections
- Microbiology laboratories, microbial test results not available through Airway Database (HelseNorge.no)
- Other statutory health registries including the Norwegian Pandemic Registry and heart registry
- Folkeregisteret and The Contact and Reservation Registry, contact information, address
- Quality Registries on Covid in Oslo University Hospital, detailed data about risk factors for Covid-19 and outcome of disease

Assessment of dietary and Supplemental Intake Questionnaire

Simple questions about the intake of vitamin D and n-3 LCPUFAs (based on a validated, selfadministered semi-quantitative food frequency questionnaire (FFQ)) will be distributed to participants at baseline. Classifying participants by baseline intake of various nutrients will allow us to evaluate whether the study agents' effects vary by such intake. Participants will be asked to complete a complete FFQ.

Questions on the use of non-study supplements or drugs containing vitamin D or EPA+DHA will be asked at baseline and end of the study and on follow-up questionnaires. We will ascertain and analyze intake from food and supplements separately, and from both sources combined.

Follow up

At the end of the intervention, three, six months, 12 and 24 months later, a questionnaire will be sent to participants. The form will be similar to the conventional follow-up questionnaires, collecting information about potential risk factors, major diseases use of medications, and medical history. The additional data will be used to address the duration of any effects seen on the primary endpoints and any side effects of the intervention as well as to explore other health effects of cod liver oil as described in the endpoint section.

Data management

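### Endpoint 3, the count of negative SARS-CoV-2 tests, is tested without covariates and no specified analysis adjusts it, so precision is given up on an endpoint with an assigned alpha of 0.001

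*SAP*

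**What the plan says.** SAP 6.1 treats endpoint 3 differently from the other primary variables: it is the total number of negative tests, not a yes/no. Appendix 1 counts them from one week after oil start to June 2, 2021. For the test, SAP 6.2 states: "The third primary variable will be compared for the two treatment groups tested using study duration-adjusted counts". It names Student's t-test, with a median test if the assumptions fail.

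The same section plans Cox regression on time to occurrence, or logistic regression on occurrence, with a listed covariate set: age, gender, BMI, occupational status, children at home, chronic disease, dietary intake and smoking. SAP 4.1 places these outside the alpha-controlled family: "Supplementary analyses, such as regression analyses, will not be part of the fallback method".

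SAP 3.3 assigns alpha 0.001 to endpoint 3. SAP 4.1 lets it grow: "Each following null hypothesis to be tested has a significance level of its stated level plus the sum of the levels of previous tests", where those tests succeeded.

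On data, the Registries list in protocol section 8 says MSIS supplies "negative and positive SARS-CoV-2 tests". It states no look-back period.

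**The concern.** How often a person is tested plausibly depends on stable features such as job, children at home and health. Baseline values of this kind can explain part of the spread in the count. Adjusting for values fixed before randomisation removes that part from the error variance, does not bias the comparison, and needs no extra participants.

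Endpoint 3 is where this is most worth having. Its assigned alpha is small, and nothing in the plan shows that its precision is ample. The Ethics section of the protocol names low Covid-19 prevalence as a significant risk and says the respiratory endpoints would still matter then. In that situation endpoints 1 and 2 are less likely to succeed and pass alpha on, and endpoint 3 would stay at 0.001.

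**Working it through.** **1. Does any specified analysis adjust the count?** The t-test and median test take no covariates. Cox regression models time to a first event and logistic regression models yes/no; neither models a total. SAP 6.2 says overdispersion will be considered where relevant, but names no count model. So the answer is no.

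**2. Alpha for endpoint 3.** The assigned levels are 0.018, 0.03 and 0.001 (SAP 3.3). Under the SAP 4.1 rule endpoint 3 is tested at 0.001 if both earlier tests fail, 0.001 + 0.018 = 0.019 or 0.001 + 0.03 = 0.031 if one succeeds, and 0.049 if both do.

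**3. The plan's own figures.** There are none for endpoint 3. For endpoint 4, SAP 3.3 gives a frequency above 30%, a 10% reduction, power above 95% with 23,000 participants, and 80% with 16,000. Take 30% against 27%, n per group, two-sided alpha 0.001 (sidedness is not stated, but two-sided fits these figures):

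power = Φ{[0.03√n − 3.2905√(2 × 0.285 × 0.715)] / √(0.30 × 0.70 + 0.27 × 0.73)}

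- n = 11,500: (3.217 − 2.101)/0.638 = 1.75, power 96.0%
- n = 8,000: (2.683 − 2.101)/0.638 = 0.91, power 81.9%
- n = 40,000 (the planned 80,000): (6.000 − 2.101)/0.638 = 6.11, power about 100%

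The stated figures reproduce, and endpoint 4 has no power left to gain at its design effect.

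**4. Gain for endpoint 3.** Let r be the (multiple) correlation between the baseline predictors and the count. It is not in the documents; 0.2 to 0.5 is assumed. Linear adjustment multiplies the variance by 1 − r², equivalent to 1/(1 − r²) times as many participants. If the unadjusted test has power P, the adjusted test has Φ{[z(1−α/2) + z(P)]/√(1 − r²) − z(1−α/2)}, with z(1−α/2) = 3.2905 at alpha 0.001 and 1.9686 at 0.049. The starting powers below are illustrative.

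| r | Variance factor | Equivalent extra participants | 50% power at 0.001 becomes | 80% power at 0.001 becomes | 50% power at 0.049 becomes |
|---|---|---|---|---|---|
| 0.2 | 0.96 | 4% | 53% | 82% | 52% |
| 0.3 | 0.91 | 10% | 56% | 85% | 54% |
| 0.4 | 0.84 | 19% | 62% | 89% | 57% |
| 0.5 | 0.75 | 33% | 69% | 93% | 62% |

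In standard deviation units, the difference detectable with 80,000 participants, 80% power and alpha 0.001 is (3.2905 + 0.8416) × √(4/80,000) = 0.0292 unadjusted. It becomes 0.0286 at r = 0.2 and 0.0253 at r = 0.5.

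**5. Is that range of r plausible for a prior test count?** Assume a gamma-Poisson model with mean m1 = 0.4 tests before and m2 = 0.8 after, and shape k. Then r = (m1·m2/k)/√[(m1 + m1²/k)(m2 + m2²/k)]. Shape 2 gives 0.22 and shape 0.5 gives 0.52. The means and shapes are assumptions, and the model takes each person's testing rate as perfectly stable, which favours a high r.

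**6. Are earlier negative tests available?** Appendix 1 codes first-time and never-positive status, and for the second primary variable describes "identifying only tests registered during the" participation period. Both suggest a wider extract. Neither shows that earlier negative tests are in it, and the only negative count defined starts after oil start.

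**The case against.** An unadjusted primary test with adjusted supplementary models is a legitimate and simple design, and it is not biased. SAP 6.2 does not ignore covariates: its list includes occupation and children at home, and protocol section 9 names Cox regression for the primary endpoints. That stands as a defence of validity. It does not reach endpoint 3's count, which those models do not fit.

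A reader might infer more than the documents support on four points.

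- **That strong predictors are known.** No correlation, R² or variance of test counts is given. The covariates listed in SAP 6.2 could fall below the assumed range: at r = 0.1 the gain is only 1/(1 − 0.01), about 1% more participants.
- **That each person's earlier negative-test count is already held.** This is an inference. First-time and never-positive status concern positive results, and the filter wording belongs to the second primary variable.
- **That endpoint 3 is always tested at 0.001.** That is the floor. At 0.049 the gains are smaller, as the table shows, and a start from 50% power is also a favourable one.
- **That endpoint 4 suffers likewise.** At the planned 80,000 its unadjusted test already has about 100% power for the stated 10% reduction. A visible gain appears only well below that effect: for a 4% reduction, power goes from 66.8% to 73.8% at an assumed R² of 0.10.

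**Conclusion.** The point holds for endpoint 3 as an avoidable loss of precision, not as an error that invalidates the test. The confirmatory comparison is unadjusted, no specified analysis adjusts the count, and candidate covariates are already collected. Under an assumed r of 0.2 to 0.5, adjustment is worth 4% to 33% more participants. The upper part of that range probably needs a prior test count, whose availability is unconfirmed. The real gain cannot be computed from the documents, because endpoint 3 has no stated rate, variance, effect or power. The figure of 80,000 is the recruitment target; the number randomised is not given.

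**What to change.** Before unblinding, in SAP 6.2:

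- Make the single confirmatory test of endpoint 3 a covariate-adjusted comparison of the counts. Either a log-link count model with a log follow-up offset and robust standard errors, or ANCOVA with robust standard errors, would serve. A median test cannot carry covariates, so it should not remain as the alternative confirmatory test.
- Use the baseline covariates already listed in 6.2, with values recorded before randomisation and a missing category where they are absent.
- Check whether the MSIS extract contains records before randomisation. If it does, add each participant's number of negative tests in a look-back window of fixed length ending at randomisation. It should not end at oil start, which is a participant-level date after randomisation and is undefined for anyone in the ITT set who never started.
- Amend SAP 4.1 so that this one adjusted model counts as the fallback test for endpoint 3, and keep the unadjusted comparison as supportive.

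Leave endpoint 4 as it is. The cost is SAP wording, slightly more analysis work and, if the records exist, one derived variable. SAP 3.3 already allows changes to the analyses before unblinding if the COVID-19 situation calls for them; this change should be recorded as an amendment with its own reason.
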